#### **8.2.1.7. Assessment of Peripheral or Central Pain**

Patients will complete a self-reported survey to evaluate the peripheral versus central nature of their pain at time points indicated in Table 1.

A copy of the survey is provided in the study reference manual.

### **8.2.1.8. Instructions for Use of Diary**

At the pre-randomization and baseline visits, patients will be instructed on the use of the NRS for scoring their walking index joint pain. Patients will be trained on the use of the diary to report their walking index joint pain NRS score and their daily acetaminophen/paracetamol use for OA and other non-OA-related reason. Retraining should occur as needed throughout the conduct of the study.

### **8.2.1.9. Patient Education Brochures**

At the pre-randomization and baseline visits, study staff will review the “Participating in a Research Study: What You Need to Know” brochure and the “Reporting Your Pain” brochure with patients to ensure they understand what a clinical study is and how to report their pain accurately. At subsequent visits, patients will be asked to review the “Reporting Your Pain” brochure themselves. At any time during the conduct of the study, patients may require retraining by study staff.

## **8.2.2. Efficacy Procedures**

### **8.2.2.1. Western Ontario and McMaster Universities Osteoarthritis Index**

The WOMAC index is used to assess patients with OA of the hip or knee using 24 parameters, and reported using a Likert scale. This index can be used to monitor the course of a disease or to determine effectiveness of study drugs. Patients will complete the WOMAC Full Survey at the time points indicated in [Table 1](#). If possible, the assessment should be administered and entered by the same person throughout the study.

A copy of WOMAC assessments will be provided in the study reference manual.

### **8.2.2.2. Patient Global Assessment of Osteoarthritis**

The Patient Global Assessment of OA is a patient-rated assessment of their current disease state on a 5-point Likert scale (1 = very good; 2 = good; 3 = fair; 4 = poor; and 5 = very poor). Patients will complete the assessment scale at the time points indicated in [Table 1](#).

A copy of the assessment is provided in the study reference manual.

### **8.2.2.3. Walking Index Joint Pain Numeric Rating Score**

Walking index joint pain intensity (scored using the NRS) will be reported by the patient each day in his or her diary, starting during the pre-randomization period through week 24. Once initial eligibility criteria are confirmed during the screening period, the investigator or designee will review the NRS with the patient at the baseline visit.

A copy of the assessment is provided in the study reference manual.

### **8.2.2.4. Work Productivity and Activity Impairment**

The work productivity and activity impairment-osteoarthritis questionnaire is a validated measure of impairments in work and daily activities ([Reilly 1993](#)) ([Zhang 2010](#)). Patients will complete the questionnaire at time points indicated in [Table 1](#).

A copy of the assessment is provided in the study reference manual.

#### **8.2.2.5. 36-Item Short Form Medical Outcomes Study Questionnaire Version 2**

The SF-36 version 2 standard is a health status measure with a 4-week recall period. The SF-36 measures eight concepts: physical functioning, role limitations due to physical health, bodily pain, general health perceptions, vitality, social functioning, role limitations due to emotional problems, and general mental health. Two summary measures of physical and mental health are constructed from the eight scales. Patients will complete the questionnaire at time points indicated in [Table 1](#). Higher scores on the scales and summary measures indicate better health status.

A copy of the assessment is provided in the study reference manual

#### **8.2.2.6. EuroQoL 5 Dimensions 5 Level Questionnaire**

The EQ-5D-5L is a standardized measure of health status developed by the EuroQoL Group to provide a simple, generic measure of health for clinical and economic appraisal. The EQ-5D-5L, as a measure of health-related quality of life, defines health in terms of 5 dimensions: mobility, self-care, usual activities, pain/discomfort, and anxiety/depression.

Each dimension has 5 ordinal levels of severity: “no problems” (1), “slight problems” (2), “moderate problems” (3), “severe problems” (4), and “unable to” (5). Overall health state is defined as a 5-digit number. Health states defined by the 5-dimensional classification can be converted into corresponding index scores that quantify health status, which ranges from <0 for states worse than dead to 1 (full health), anchoring dead at 0. Patients will complete the questionnaire at time points indicated in [Table 1](#).

A copy of the assessment is provided in the study reference manual.

#### **8.2.2.7. Healthcare Resource Utilization Questionnaire**

The HCRU questionnaire is a tool designed to capture, over a preceding three-month period, healthcare utilization events that are not collected as part of the safety assessments in the current study. Examples of these types of events include a patient's use of walking aid, emergency room visits, and unscheduled physician office visits. Sites will complete the questionnaire at time points indicated in [Table 1](#). The overall healthcare resource use will be computed based on responses to the healthcare resource utilization questionnaire as well as any hospital visits that are captured in the safety database.

A copy of the assessment is provided in the study reference manual.

#### **8.2.2.8. Treatment Satisfaction Questionnaire for Medication**

The TSQM questionnaire is a standardized instrument to assess patients' satisfaction with medication. The questionnaire provides scores on 4 domains – side effects, effectiveness, convenience, and global satisfaction. Patients will complete the TSQM at time points indicated in [Table 1](#).

A copy of the assessment is provided in the study reference manual.

### **8.2.3. Safety Procedures**

#### **8.2.3.1. Vital Signs**

Vital signs, including body temperature and respiratory rate, will be collected predose at time points according to [Table 1](#). Blood pressure and heart rate will be collected as part of the orthostatic hypotension assessments. If at any visit after the randomization visit the pulse is less than 45 bpm, an ECG with rhythm strip will be obtained to confirm the heart rate and rhythm.

#### **8.2.3.2. Physical Examination**

A thorough and complete physical examination will be performed at time points according to [Table 1](#). Care should be taken to examine and assess any abnormalities that may be present, as indicated by the patient's medical history. Measurements of patient height and weight should be recorded at the time points indicated in [Table 1](#).

#### **8.2.3.3. Assessment of Orthostatic Blood Pressure and Heart Rate**

An assessment of orthostatic blood pressure will be conducted at the time points indicated in [Table 1](#). The assessments should be conducted as per the instructions in the study manual. A patient will be determined to have orthostatic hypotension if any of the following criteria are met:

If the supine blood pressure is <160 mmHg systolic, a decrease in either the 1 or 3 minute standing systolic blood pressure of  $\geq 20$  mmHg or a decrease in the standing diastolic blood pressure of  $\geq 10$  mmHg from the supine systolic or diastolic blood pressure, respectively

OR

If the supine blood pressure is  $\geq 160$  mmHg systolic, a decrease in either the 1 or 3 minute standing systolic blood pressure of  $\geq 30$  mmHg or a decrease in the standing diastolic blood pressure of  $\geq 15$  mmHg from the supine systolic or diastolic blood pressure, respectively

OR

An increase in either the 1 or 3 minute standing heart rate of  $\geq 30$  bpm from the supine heart rate

OR

The patient is unable to stand for either one of the standing blood pressure measurements due to dizziness or lightheadedness

If the initial assessment for orthostatic hypotension is consistent with the above definition, the supine and standing blood pressures and/or pulse should be repeated as outlined above, up to 2 more times.

#### **8.2.3.4. Joint Pain Questionnaire**

A joint pain questionnaire will be completed by the patient at the time points indicated in [Table 1](#). For each knee, hip, and shoulder joint, the patient will be prompted to indicate if he or she has experienced pain. A patient report of having experienced pain will serve as a tool to prompt further evaluations as deemed necessary by the investigator.

A copy of the assessment is provided in the study reference manual.

### 8.2.3.5. Survey of Autonomic Symptoms

Signs and symptoms of autonomic dysfunction will be assessed by the investigator at time points indicated in Table 1. If possible, the assessment should be completed by the same person throughout the study. A patient report of having experienced symptoms of autonomic dysfunction will serve as a tool to prompt further evaluations as deemed necessary by the investigator.

A copy of the survey is provided in the study reference manual.

### 8.2.3.6. Neurologic Examination

A full or a brief neurological examination will be performed at the time points indicated in Table 1. Neurological findings at baseline that are not exclusionary should be recorded in the medical history. Findings at subsequent visits will be assessed by the investigator to determine if these should be recorded as an AE.

The neurological examination will cover the following domains: motor, sensory, cranial nerves, reflexes, and coordination/balance and assessment for presence/absence of signs of carpal tunnel syndrome and may be conducted by any clinician at the site qualified to do so. Whenever possible, the same clinician who conducts the baseline neurological examination should continue to conduct the examinations on a given patient. The investigator may refer patients with persistent or worsening neurologic symptoms for a neurologic consultation, if clinically indicated. Additional neurologic assessments will include nerve conduction studies and other tests as deemed clinically necessary in the judgement of the neurologist.

Complete guidance on how to conduct the full and the brief neurologic examination is provided in the study reference manual.

### 8.2.3.7. Imaging

Radiographs of the large joints (knees, hips, and shoulders) will be taken using a standard approach at the time points indicated in Table 1. An MRI of the index and contralateral joint must be performed at screening. MRIs will also be performed on any hip or knee joint with a K-L score of  $\geq 3$ . Radiographs and possibly an MRI will be performed on any joint following a report of clinically significant worsening or exacerbation of pain in that joint. An X-ray and an MRI should also be performed pre-operatively if a patient is to have a JR during the study. Event based and pre-operative images will be submitted for adjudication. Detailed procedures will be provided in a separate manual provided by the central imaging center. Radiograph or MRI will be sent to a central reader, where the images will be digitized.

#### **Radiographs**

Weight-bearing (standing) posterior-anterior radiographs of both knees in the semi-flexed position, and anterior-posterior radiographs of both hips and both shoulders, will be conducted at these visits. Additional instructions for positioning of joints are provided in the study reference manual.

Radiographs of the knees, hips, and shoulders will be sent to a central reader and evaluated to confirm no evidence of AA such as rapidly progressive osteoarthritis type 1 or 2, subchondral insufficiency fracture, or osteonecrosis.

#### **MRI**

During screening, MRIs of the index and contralateral joint as well as joints with a K-L score  $\geq 3$  will be sent to a central reader to confirm that there is no evidence of an exclusionary feature. Confirmation that there are no exclusionary findings on MRI must be received before a patient can be randomized. An MRI of any joint will be considered if radiographs taken after randomization suggest the presence of an abnormal process inconsistent with normal progression of OA, as determined by the investigator or central reader.

At the end of study phone contact, patients who had an AA will have an MRI performed of the affected joint(s). If the affected joint has undergone JR an X-ray may be substituted for an MRI.

Refer to the supplemental imaging manuals for data collection and management procedures.

#### **8.2.3.8. Electrocardiogram**

A standard 12-lead ECG will be performed at the time points indicated in [Table 1](#), with the patient in the supine position for approximately 5 minutes and prior to blood samples being drawn. Heart rate will be recorded from the ventricular rate, and the PR, QRS, and the QT and QTc intervals will be recorded. The ECG data will be read by a central reading center. Detailed procedures will be provided in a separate manual provided by the central reading center.

#### **8.2.3.9. End of Study Phone Contact**

An end of study phone contact will be conducted at 52 weeks following the last dose of SC study drug. Patients will be asked whether they underwent JR surgery following the last in-clinic visit of the follow-up period or whether they are scheduled (or on a waiting list) for JR surgery. Patients who had JR surgery will also be asked to submit pre-operative imaging (X-ray and MRI, if available) for adjudication. Patients who had an AA will have an MRI performed of the affected joint(s). If the affected joint has undergone JR an X-ray may be substituted for an MRI.

#### **8.2.3.10. Procedures to be Performed Only in the Event of a Joint Replacement Surgery**

In the event that a patient must undergo JR surgery during the treatment or follow-up periods, the patient will be discontinued from study drug and asked to return for a pre-operative visit. The pre-operative visit should be completed before JR surgery if possible and pre-operative images will be submitted to the adjudication committee for review. Following the JR surgery, the patient will complete follow-up safety evaluations at 4 weeks and 20 weeks after surgery (see [Table 2](#)).

In the event that the pre-operative visit is not performed, standard-of-care pre-operative images of the joint with JR must be obtained and submitted to the central imaging vendor's adjudication committee for review. Imaging of all other joints per the pre-operative visit procedures will be done post-operatively at the first JR follow-up study visit (4 weeks after surgery) if not done before surgery.

All available medical history/information for patients who undergo JR surgery must be collected, including placement of prosthesis, healing of the surgical wound and the results of histopathologic examination.

Full details of these assessments are provided in the study reference manual.

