### 7.3.2.1. Reasons for Permanent Discontinuation of Study Drug

Study drug dosing will be permanently stopped in the event of any of the following:

- A patient who is currently enrolled under an earlier version of this protocol must be immediately discontinued from study drug, undergo all end of treatment visit assessments and move directly into the 20-week safety follow-up period under this version of the protocol, if they meet any of the following conditions that were excluded after re-evaluating the safety profile of NSAIDs:
  - a) They have a known medical history (at any time) of peripheral vascular disease, transient ischemic attack, cerebrovascular accident, myocardial infarction, unstable angina, or documented atherosclerotic cardiovascular disease; or
  - b) They have a known GFR <30 mL/minute/1.73 m^2 or,
  - c) They are currently taking combination therapy of a diuretic with either an ACE inhibitor or ARB (Note: Patients may remain in the study if they are willing and able to change their antihypertensive regimen such that they are no longer on a combination of a diuretic with either an angiotensin-converting enzyme (ACE) inhibitor or angiotensin receptor blocker (ARB))
- A patient who was randomized under an earlier version of the protocol to 3 mg SC Q4W or 6 mg SC Q8W fasinumab
- A patient developing clinically significant peripheral sensory or motor neurologic events confirmed by a neurologist's examination and graded by the neurologist as at least moderate peripheral neuropathy limiting activities of daily living, ie, grade ≥2 according to Common Terminology Criteria for Adverse Events (CTCAE) v.4; study sites should use CTCAE v.4 criteria throughout the study for consistency
- Evidence of pregnancy
- A patient developing new or worsening signs and symptoms indicative of carpal tunnel syndrome
- Continued non-compliance with protocol-defined maximum acetaminophen/paracetamol use (with a maximum daily dose of 2500 mg [countries where 500 mg strength tablets/capsules are available] or 2600 mg [countries where 325 mg strength tablets/capsules are available]) during the treatment and follow-up periods, after appropriate counseling
- Continued non-compliance with the protocol, including usage of NSAIDs that are not permitted in the study, after appropriate counseling
- Joint replacement surgery

- Adverse events of special interest (AESIs) of:
  - Adjudicated arthropathy, as described in Section 9.6.1.1

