**8.1.1. Footnotes for the Schedule of Events Table**

1. Patients who discontinue study medication before week 24 will be encouraged to follow the visit schedule through the remainder of the study. If a patient chooses to end study participation, he or she will be asked to return to the clinic as soon as possible for an early termination visit. Imaging assessments need to be repeated if it has been >30 days since the joints were last imaged. If it has been ≤30 days since imaging assessments were completed, imaging assessments may be completed at the discretion of the investigator.
2. HIV and/or hepatitis testing will be performed on a country-by-country basis, according to local guidelines if required by regulatory authorities or ethics boards
3. Only for patients who provide written informed consent for the optional genomics sub-study. The sample should be collected at the day 1 (baseline/randomization) visit, but may be collected at any visit during the study after a patient has been randomized.
4. At the screening and pre-randomization visits, study staff will review the “Participating in a Research Study: What You Need to Know” brochure and the “Reporting Your Pain” brochure with patients to ensure they understand what a clinical study is and how to report their pain accurately. At subsequent visits, patients will be asked to review the “Reporting Your Pain” brochure themselves. At any time during the conduct of the study, patients may require retraining by study staff.
5. Subcutaneous study drug administration will be the last procedure at each dosing visit, and will be done after all laboratory, PK, ADA and research samples have been collected and all study assessments performed. Patients will be observed in the clinic for approximately 1 hour after SC study drug is administered.
6. Use of study-provided rescue medication will be recorded daily using diaries. Acetaminophen/paracetamol use will be reported from pre-randomization visit to week 24.
7. Patients will complete the WOMAC pain subscale for both hips and knees at the screening visit. Then, the WOMAC Full Survey will be completed only for the index joint at subsequent visits.
8. Walking index joint pain NRS score will be recorded by the patient each day using their diary, starting during the pre-randomization period through week 24. Walking index joint pain NRS score will be recorded by the patient at the site at the week 24 visit.

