#### 9.6.1.4. Joint Replacement Surgery

An end of study phone contact will be conducted at 52 weeks following the last dose of study drug to evaluate the number of patients who have undergone or are scheduled for JR surgery as described in Section 8.2.3.9. Any elective JR surgery planned before completion of the ICF would be part of the exclusion criteria and would not be considered an AE.

After signing of the ICF, report JR surgery as an AESI if the JR surgery is an elective event that is not associated with a new/worsening AE.

Do not report JR surgery as an AE/AESI if the JR surgery is for the treatment of a new or worsening AE. In this case, the new or worsening AE should be the reported AE/AESI term.

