## 10.2. Justification of Sample Size

Assuming a 2-sided alpha level 0.05 and a 20% dropout rate up to week 24, an enrollment of 600 patients in the fasinumab 1 mg Q4W group and 300 patients in the placebo group will provide at least 99% power to detect an effect size of 0.46 in the WOMAC pain and physical function subscale scores (ie, absolute treatment difference of 1.1 between fasinumab and placebo with a SD of 2.4). The assumed treatment difference and standard deviation (SD) are based on results from study R475-PN-1227. The sample size will provide 99% power to detect an effect size of 0.36 in PGA (ie, absolute treatment difference of 0.4 with a SD of 1.1, R475-PN-1227).

Assuming a 2-sided alpha level 0.05 and a 20% dropout rate up to week 24, an enrollment of 600 patients in the fasinumab 1 mg Q4W group and the pooled NSAIDs group will provide approximately 92% power to detect an effect size of 0.22 in the WOMAC pain subscale (ie, absolute treatment difference of 0.51 with a SD of 2.3, [Schnitzer 2015]). The sample size will provide 95% power to detect an effect size of 0.24 in WOMAC physical function subscale (ie, absolute treatment difference of 0.50 with a SD of 2.1, [Schnitzer 2015]), and 79% power to detect an effect size of 0.18 in PGA (ie, absolute treatment difference of 0.18 with a SD of 1.0 [Ekman 2014]).

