### 5.7.1. Analysis of Primary Efficacy Variable(s)

The co-primary efficacy variables are:

1. Change in the WOMAC pain subscale scores from baseline to week 24
2. Change in the WOMAC physical function subscale score from baseline to week 24

The following hypotheses will be tested:

- $H_1$ : There is no treatment difference between fasinumab 1 mg Q4W and placebo in WOMAC pain or physical function subscale at week 24 versus there is treatment difference in WOMAC pain and physical function subscale score at week 24

For  $H_1$ , the estimand is the difference in means between the fasinumab 1 mg Q4W dose+ protocol-defined rescue medication and placebo+ protocol-defined rescue medication in the change from baseline to week 24 in the WOMAC pain and physical function scores in the FAS, regardless of whether or not rescue medication or prohibited medication had been taken. Any data collected after discontinuing treatment will not be used in the primary efficacy analysis, but used in a treatment policy sensitivity analysis.

The co-primary efficacy variables will be analyzed separately using a multiple imputation approach with a mixed-effect model for repeated measures (MMRM) based on the FAS. For patients who discontinued treatment due to lack of efficacy or AEs or deaths, their missing WOMAC subscale scores after discontinuation will be imputed with values centered at the mean baseline WOMAC subscale score of the treatment group that the patient was randomized to. For patients who discontinued treatment due to other reasons including discontinuation because of public health measures implemented in response to COVID-19, their missing WOMAC subscale scores after discontinuation will be imputed under the missing-at-random assumption using the regression method with adjustment for covariates including treatment group, randomization strata (K-L category [2 to 3, or 4], index joint [knee, hip], and geographical region [Other, Europe, North America]) and baseline WOMAC subscale score. Intermittently missing WOMAC subscale scores prior to treatment discontinuation will be imputed using the Markov Chain Monte Carlo method.

Missing data up to week 24 will be imputed 50 times to generate 50 complete data sets by using the SAS procedure PROC MI following the 3 steps below:

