#### Analysis of Treatment Policy Estimand

Sensitivity analysis of the treatment policy estimand for the co-primary endpoints will be performed using similar analysis methods as the primary efficacy analysis. The treatment policy estimand is the difference in means between each fasinumab dose+ protocol-defined rescue medication and placebo+ protocol-defined rescue medication in the change from baseline to week 24 in the WOMAC pain and physical function scores based on the FAS, regardless of study treatment discontinuation prior to week 24 and regardless of whether or not rescue medication or prohibited medication had been taken. Hence, data from all patients, including

data collected after discontinuing treatment up to week 24 will be used in this sensitivity analyses. Missing WOMAC subscale scores up to week 24 will be imputed using the same approach as in Section 5.7.1.

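### Joint replacement forces a stop of study drug, but the SAP does not say which imputation rule that stop follows, so a replaced index joint can keep on-drug benefit in the co-primary analysis and count as a response in H3

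*Protocol*

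**What the plan says.** **Stopping.** Protocol 7.3.2.1 gives "Joint replacement surgery" its own bullet among the reasons for permanent discontinuation of study drug. Section 8.2.3.10 repeats the rule: "In the event that a patient must undergo JR surgery during the treatment or follow-up periods, the patient will be discontinued from study drug".

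**Reporting.** Under Protocol 9.6.1.4 an elective JR not linked to a new or worsening AE is reported as an AE of special interest (AESI). SAP 4.6.2 flags it by a tick box on the AE page. For other JRs the instruction is "Do not report JR surgery as an AE/AESI if the JR surgery is for the treatment of a new or worsening AE"; the underlying AE is the reported term.

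**Primary imputation.** SAP 5.7.1 discards scores collected after treatment stops and imputes them. Stops for lack of efficacy, AE or death are re-centred at the arm's baseline mean in Step 3. The remaining group begins "For patients who discontinued treatment due to other reasons including discontinuation because of public health measures implemented in response to COVID-19" and is imputed under MAR. The tipping-point Step 3 adds its delta for the same three reasons only.

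**Other analyses.** H2 and H4–H6 use the same method (SAP 5.7.3). H3 is a Cochran-Mantel-Haenszel test in which missing data are non-response. SAP 10.1 lists the analysis that makes all treatment stoppers non-responders as a sensitivity analysis only. In the treatment-policy analysis, "data collected after discontinuing treatment up to week 24 will be used in this sensitivity analyses".

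**Collection after JR.** Protocol Table 2, the post-JR schedule, has no WOMAC or PGA. Patients who stop drug are encouraged to keep the Table 1 visits, which do include WOMAC: "Then, the WOMAC Full Survey will be completed only for the index joint at subsequent visits".

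**The concern.** Replacement of the index joint is hard to read as anything but failure of the pain treatment in that joint, and all-cause JR is a named safety endpoint. The return-to-baseline rule exists so that patients who fail treatment are not credited with the benefit they had, or would have had, on drug. JR is a stop that the protocol itself requires, yet whether the rule reaches it depends on which discontinuation reason a site ticks. Two patients with the same operation can be imputed by different rules, and the tipping-point analysis cannot expose this because its delta covers the same three reasons.

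The comparisons affected are the co-primary pair, H2 and H4–H6. H3, tested first after H1, has a related gap: a good week-24 score on a prosthetic joint would be a response.

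**Working it through.** **1. The plan's own power figures.** Protocol 10.2 starts from "Assuming a 2-sided alpha level 0.05 and a 20% dropout rate up to week 24" and states that "an enrollment of 600 patients in the fasinumab 1 mg Q4W group and 300 patients in the placebo group will provide at least 99% power". With 20% removed (480 v 240 against placebo, 480 v 480 against NSAIDs) and a normal approximation:

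| Comparison | Difference, SD | Stated | Recomputed |
|---|---|---|---|
| WOMAC v placebo | 1.1, 2.4 | at least 99% | 99.99% |
| PGA v placebo | 0.4, 1.1 | 99% | 99.6% |
| Pain v NSAIDs | 0.51, 2.3 | about 92% | 93.0% |
| Function v NSAIDs | 0.50, 2.1 | 95% | 95.8% |
| PGA v NSAIDs | 0.18, 1.0 | 79% | 79.6% |

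The sample size is not at fault.

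**2. What the coding changes.** Step 3 takes the MAR value from Step 2 and subtracts the arm's mean change from baseline in on-treatment patients at that visit. Before truncation to 0–10, the two codings therefore differ by exactly that mean change, whatever the patient's earlier scores.

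Let p be the fraction of an arm with an index-joint JR stop before week 24 recorded under another reason, and m the arm's mean improvement, for fasinumab (f) and comparator (c). Then:

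shift in the difference = p_f × m_f − p_c × m_c (positive favours fasinumab)

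**3. Assumed inputs.** The documents give neither p nor m. I take p_f of 1–3%, p_c of 0.5–1% and m_f of 1–4 points. I set m_c to m_f minus the planned difference, so for NSAID pain at m_f = 3, m_c = 3 − 0.51 = 2.49. Power is recomputed as if the planned 0.51 included the credit.

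| p_f, p_c, m_f | Shift, pain v NSAIDs | Difference left | Power |
|---|---|---|---|
| 1%, 0.5%, 1 | 0.0100 − 0.00245 = 0.008 | 0.502 | 92.3% |
| 1%, 0.5%, 3 | 0.0300 − 0.01245 = 0.018 | 0.492 | 91.3% |
| 1%, 1%, 3 | 0.0300 − 0.0249 = 0.005 | 0.505 | 92.5% |
| 3%, 1%, 3 | 0.0900 − 0.0249 = 0.065 | 0.445 | 85.0% |
| 1%, 3%, 3 (rates reversed) | 0.0300 − 0.0747 = −0.045 | 0.555 | 96.2% |
| 3%, 0%, 4 (outer bound) | 0.1200 − 0 = 0.12 | 0.39 | 74.8% |

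Equal JR rates still give a small shift towards the arm with the larger mean improvement. At m_f = 3 the sign reverses only when the NSAID rate exceeds 3/2.49 = 1.2 times the fasinumab rate.

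For function v NSAIDs, the 3%, 1%, 3 case gives 0.0900 − 0.0250 = 0.065. The difference falls from 0.50 to 0.435 and power from 95.8% to 89.4%.

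**4. H1.** At the outer bound, 1.1 − 0.12 = 0.98 remains. The smallest significant difference is 1.96 × 2.4 × √(1/240 + 1/480) = 0.37, and power stays above 99.9%.

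**5. H3.** A JR patient without a week-24 score is already a non-responder. The gap concerns those with a score from a continued Table 1 visit. If every fasinumab JR patient had a responding score and no placebo patient did, the response difference would move by p_f, or 1–3 percentage points. That is an upper limit.

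H2 and H6 follow the same formula on the PGA scale. I have not sized them, because an assumed PGA change by arm would be needed.

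**The case against.** **JR may reach the re-centred group anyway.** Every JR should leave an AE-type record: elective JR as an AESI on the AE page, other JRs under the underlying AE. The eCRF discontinuation categories are not in the documents. A separate bullet in Protocol 7.3.2.1 does not prove separate coding either, since hepatotoxicity and gastrointestinal bleeding also have their own entries and are clearly AEs. This stands: a reader might infer that JR stops always go to MAR, and the documents do not show that. But AE reporting and the recorded reason for stopping treatment are different items, and nothing links them for JR.

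**MAR uses the patient's own history.** Step 2 conditions on earlier scores, so a patient who worsened before surgery is not simply given the arm's average course. This is true of the imputed level, but it does not remove the gap between the two codings. The WOMAC at the JR pre-operative visit may also be lost to the primary analysis if the stop is dated before that visit.

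**Direction.** A reader might infer that the arm with more replacements always gains. Step 3 uses each arm's own mean change, so the sign depends on both products.

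**Treatment policy.** A reader might call post-surgical scores an error in that analysis. Using data regardless of discontinuation is its definition, and replacing observed scores would change the estimand. Table 2 collects no WOMAC, so such scores exist only if Table 1 visits continue.

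**Relevance.** The Data Monitoring Committee's concern about time to joint replacement came from another study and led to stopping 3 mg Q4W and 6 mg Q8W. The protocol reports the committee's support for 1 mg Q4W. No JR excess at 1 mg is documented, and patients already scheduled for JR are excluded.

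**Conclusion.** The gap is real. The protocol requires a stop for JR, and the SAP lets an unspecified coding choice decide whether the replaced index joint is returned to baseline or may keep on-drug benefit. The tipping-point analysis has the same gap, and the main H3 analysis can count an observed score on a replaced index joint as a response. The H3 reading is partly an inference: a separate sensitivity analysis for stoppers would add little if their post-stop scores were already treated as missing.

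The size rests wholly on assumed JR rates and mean changes. It is probably small. H1 is safe throughout the range. For H4 and H5 the effect is modest at most within the 1–3% and 0.5–1% rates at a 3-point improvement; the 0.12-point bound needs 3% of fasinumab patients, no NSAID patients and 4 points. The documents do not support reading this as a demonstrated bias towards fasinumab.

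**What to change.** Before database lock:

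- In SAP 5.7.1, in the text and in Step 3, add replacement of the index joint before week 24, whatever discontinuation reason is recorded, to the group re-centred at baseline. H2 and H4–H6 inherit the rule.
- Add the same event to the tipping-point Step 3, so that the delta covers it.
- In SAP 5.7.3 and 5.7.5, count index-joint replacement before week 24 as non-response in H3 and the other responder analyses.
- Keep the treatment-policy analysis as defined, and show it with and without index-joint scores obtained after replacement.

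The cost is SAP wording and some programming; JR date and affected joint are already needed for the planned JR summaries. The fasinumab estimate may become slightly less favourable.
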